The target enrollment for the study is 1,462 Veterans. If recruitment is not proceeding at an appropriate rate, the Principal Investigator and the Study Biostatisticians will scrutinize the reasons for participant exclusions and other barriers to recruitment. Based on this information, the Executive Committee may choose, with the approval the Director, VA CSR&D, to drop centers or add additional centers, or with the concurrence of the DMC, and the Director CSR&D make modifications to the inclusion/exclusion criteria, or extend the recruitment period in some or all centers and/or to extend the total length of the study.

Medical centers will only be allowed to continue in the study if adequate participant intake is maintained. The target recruitment for each VA site is 17 participants per year (approximately 1 every 3 weeks). Because there is usually a ramp-up in recruitment early on, during the main study phase, sites that do not enroll at least four participants during their first six months, or twelve participants within the first year, will be considered for probation or reduction in funding. Since the Pilot study will be operating at six sites selected on the basis of projected high recruitment, all sites within the Pilot study must meet at least 90% of the target enrollment of 17 patients within the first year; satisfaction of this recruitment criteria by these "vanguard" sites

will provide evidence of study feasibility in full-scale operation over a wider range of sites. If a medical center is placed on probation, the Principal Investigator and Study Biostatistician confer with the site personnel and, if necessary, visit the site to help improve the rate of recruitment. If there is no improvement in accrual after the probation period, the site may be subject to reduced funding or possible termination as a study site. The Executive Committee only takes actions leading to discontinuation of a center with the concurrence of the Director, VA CSR&D. If a center is terminated from the trial, resources are reallocated to other centers or used to start up a backup site.

E. Monitoring Medical Center Performance

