The American College of Cardiology and American Heart Association have established guidelines for device based therapy to include a class I indication of ICD therapy for primary prevention of sudden cardiac death in patients with New York Heart Association class II or III symptoms, ischemic and non-ischemic heart disease and left ventricular ejection fraction (LVEF) of 30% or less, who are receiving long-term optimal medical therapy and have a reasonable expectation of survival with good functional status for greater than 1 year⁸. While it is difficult to determine “long-term optimal medical therapy” and “expectation of survival” from the electronic patient records database, it is possible to identify heart failure patients who may qualify for ICD implantation.

b) Estimating Candidacy from the Patient Records Database

Based on the stated criteria for implantation of an ICD, the primary diagnosis by which study-eligible patients can be identified is that of Systolic Heart Failure (SHF). Additionally, a large segment of patients with a Congestive Heart Failure (CHF) diagnosis may also be eligible, however due to the inconsistencies in diagnostic and coding practices within heart failure patients^{128,129}, it may be difficult to estimate the exact proportion of CHF patients who meet the implantation criteria. Several surveys report the proportion of CHF patients with low ejection fraction (LVEF \leq 30%) at 22-47% of the CHF population (Table 16).

Table 16. Proportion of non-systolic heart failure patients with suppressed ejection fraction.		
Ejection Fraction	Proportion of CHF patients	Source
$\leq 30\%$	47%	Hallstrom, 1995 ¹³⁰
$< 30\%$	30%	Nieminen, 2006 ¹³¹
$< 30\%$	29%	Tavazzi, 2006 ¹³²
$< 30\%$	22%	Cohen-Solal, 2000 ¹³³

For the purposes of estimating the volume of potential candidates for this study, we shall adopt the assumption of eligibility for 100% of SHF patients and 30% of all CHF patients (a conservative estimate based on Table 16).

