6.	Cincinnati	388	31	26	1
7.	Cleveland	1015	88	18	2
8.	Columbia	625	45	21	4
9.	Dallas	1127	150	32	3
10.	Atlanta	700	69	17	4
11.	Durham	415	45	13	0
12.	Gainesville	1081	91	31	5
13.	Hines	577	68	3	1
14.	Houston	760	88	6	3
15.	Indianapolis	524	44	15	2
16.	Kansas City	1626	99	39	6
17.	Little Rock	612	73	5	2
18.	Lexington	454	39	3	1
19.	Louisville	424	56	13	3
20.	Milwaukee	589	35	21	0
21.	Minneapolis	850	72	54	10
22.	Nashville	739	87	34	8
23.	New York	424	66	29	10

24.	Oklahoma	673	67	1	0
25.	Omaha	1308	111	11	1
26.	Palo Alto	536	39	21	1
27.	Philadelphia	675	46	14	3
28.	Pittsburgh	577	68	12	3
29.	Portland	735	42	61	6
30.	Richmond	395	47	35	3
31.	St. Louis	1411	78	26	4
32.	Salt Lake City	660	32	18	3
33.	San Diego	529	50	4	3
34.	San Francisco	335	20	8	1
35.	Tampa	652	71	57	12
36.	Tucson	518	28	24	3
37.	Washington, DC.	292	15	2	0
38.	West Los Angeles	628	33	15	1
39.	West Palm Beach	609	59	3	2
40.	West Roxbury	594	40	22	4
	Total (Top-20)	18,353	1,514	537	84
	Total (Top-27)	22,364	1,873	623	102
	Total (Top-30)	23,929	1,977	673	104
	Total (Top-40)	27,956	2,352	828	125

FY2009 data summary: 44,713 records across 130 sites. Top sites selected by # CHF+ ICD–.

Thus, assuming that among congestive heart failure patients, 30% qualify by sufficiently low ejection fraction, then there are over 6,000 heart failure patients meeting the minimum criteria for ICD eligibility in the 30 largest candidate sites (as given by the number of CHF patients without ICD), without accounting for adequate medical therapy and survivability. This is likely a moderate underestimate of the total number of available patients, as this number reflects patient visits in FY2009, i.e. there may be many eligible patients who did not appear in the patient registry in FY2009

d) Not-previously-seen Patients

It is likely that eligible patients will continually present to the study centers over the three years of enrollment. We estimate the number of newly presenting patients at the 27 enrolling sites throughout the enrollment period. Table 19 displays the number of unique patients in FY2009 with SHF (top row) and CHF (but not SHF, bottom row), as found in FY 2009 (left column), followed by patients not seen at all in before FY2010 (next column).

Table 19. Newly presenting patients in 2008-2010. Recruitment pools summed over years.				
DX Code	2008	2009	2010	3 years
CHF+, ICD-	123,580	57,872	48,379	229,831
CHF+, ICD- (× 30%)	37,074	17,362	14,514	68,950
SHF+, ICD-	2,125	1,657	1,941	5,723

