Subtotal (i.e. Across VA)	39,199	19,019	16,455	74,673
Subtotal (30% adj. top-27)	19,600	9,510	8,228	37,337
Top-N adjustments: Proportion of Across-VA patient pool within the top-N sites (ref. previous table): Top-27: 22,364 ÷ 44,713=50.0%.				

Using these data we estimate that there will be approximately 37,000 unique Veterans eligible for the trial at the 27 participating sites. This was estimated based on a 3-year running total of 5,723 patients with documented systolic heart failure without an ICD (SHF+, ICD-) and a total population of chronic heart failure patients without ICD (and not double-counting those with SHF) of 229,831, of which there are an estimated 30% (=68,950) truly eligible for this study, we project a patient pool of 74,673 patients across all VAMCs. We estimate that a study comprising 27 of the top-implanting sites would avail this study to approximately 50% of the VA heart failure population (37,337).

e) Summary

The available pool of patients ≥ 70 years was estimated by two independent methods: 1) pulling of patient records from the National Data Service for all in- and outpatient visits made in 2010, identifying patients with heart failure + ICD, and 2) extraction of the total number of ICD procedures performed in the VA from the Cardiac Surveillance Database. From these data sources, we estimate there to be nearly 37,000 patients available for study across 27 sites in a 3-year recruitment period. The average number of heart failure patients being seen at each of the 27 selected participating sites is estimated to be more than 440 Veterans per year. Whereas we target a sample size of $N=1,462$, this equates to an enrollment rate of approximately 3.7% of the potentially eligible patient pool.

< This page left intentionally blank >

XVII. GOOD CLINICAL PRACTICES

A. Role of Good Clinical Practices

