37. Schroll, J. B., Maund, E. & Gøtzsche, P. C. Challenges in Coding Adverse Events in Clinical Trials: A Systematic Review. *PLoS ONE* **7**, e41174 (2012).
38. Gajewski, B. J., Simon, S. D. & Carlson, S. E. Predicting accrual in clinical trials with Bayesian posterior predictive distributions. *Stat. Med.* **27**, 2328–2340 (2008).
39. Peto, R. *et al.* Design and analysis of randomized clinical trials requiring prolonged observation of each patient. I. Introduction and design. *Br. J. Cancer* **34**, 585–612 (1976).

<This page left intentionally blank>

5. Reporting Tables

Table 1: Cumulative Number of Subjects Pre-screened, Enrolled, and Randomized by month

Date	Number of Patients pre-screened	Number of Participants Enrolled	Number of Participants Randomized	Expected Number of Randomizations
05/2015				
06/2015				
07/2015				
08/2015				
⋮				

Table 2: Total Number of Subjects Pre-screened, Enrolled and Randomized by Site

Site	Number of Patients Pre-screened	Number of Participants Enrolled	Number of Participants Randomized	Expected Number of Randomizations
Gainesville, FL(573)				
Minneapolis, MN (618)				
Nashville, TN (626)				
Palo Alto, CA (640)				
Portland, OR (648)				
Washington, DC (688)				

Table 3: Summary of Inclusion and Exclusion Criteria and Pre-Screening Status – All Pre-Screened Subjects with Age ≥ 70 , eligible for implantation and with OMT

	N (%)
No. of Pre-Screened Subj who meet Inclusion Criteria and Eligibility determined	
No. of Pre-Screened Subj. who meet Inclusion Criteria but not eligible	
Enrolled in or planning to enroll in a conflicting trial	
Receiving a bi-ventricular ICD device	
NYHA class IV heart failure	
Cardiogenic shock or symptomatic hypotension while in stable baseline rhythm	
Coronary artery bypass graft (CABG) or percutaneous transluminal coronary angioplasty (PTCA) within the past 3 months	
An MI within the past 40 days	
Clinical symptoms or findings that would make them a candidate for coronary revascularization	
Irreversible brain damage from pre-existing cerebral disease	
Any disease other than cardiac disease (e.g. cancer, uremia, liver failure), associated with a likelihood of survival less than 1 year	
Circumstance that would prevent completion of the trial and follow-up activities, including medical condition	
No. of Pre-Screened Subj who meet Inclusion Criteria and are Eligible	
Final: Enrolled in study	
Final: Eligible but will not enroll	
Ongoing: Eligible & planning to enroll;	

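### Does the protocol's own site table contradict the claim that the six Pilot sites were chosen for projected high recruitment?

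*Combined protocol and SAP*

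**What the plan says.** Protocol XII.D sets one recruitment figure for every site: "The target recruitment for each VA site is 17 participants per year". For the Pilot it adds that, because the six were "sites selected on the basis of projected high recruitment, all sites within the Pilot study must meet at least 90% of the target enrollment", each must reach that mark within the first year. Meeting it "will provide evidence of study feasibility in full-scale operation over a wider range of sites". Ninety per cent of 17 is 15.3, so the mark is 16 patients.

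The only site-level data are in protocol XVI.A.1.c, Table 18, which lists heart-failure patients aged 70 or older, with and without an ICD, at 40 centres. Its footnote reads "FY2009 data summary: 44,713 records across 130 sites. Top sites selected by" the count of congestive heart failure (CHF) patients without an ICD. XVI.A.1.b converts counts to an eligible pool: "we shall adopt the assumption of eligibility for 100% of SHF patients and 30% of all CHF patients", where SHF is systolic heart failure. XVI.A.1.d bases the feasibility estimate on 27 sites: "We estimate that a study comprising 27 of the top-implanting sites would avail this study to approximately 50% of the VA heart failure population".

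SAP section 5 contains a shell headed "Table 2: Total Number of Subjects Pre-screened, Enrolled and Randomized by Site". It lists Gainesville, Minneapolis, Nashville, Palo Alto, Portland and Washington, with a blank column for expected randomizations. The SAP does not label these as Pilot sites. That is inferred from the count of six and from the 05/2015 start of the Table 1 shell.

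**The concern.** The every-site mark is argued from the way the sites were chosen, yet the protocol's own counts seem to support that argument for only four of the six. Palo Alto is in the lower half of the list and Washington is at the bottom, outside the 27 sites behind the feasibility estimate. No site-specific projection appears in the supplied text.

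The Pilot exists to judge recruitment. Protocol XII.B has the DMC compare actual with projected rates, XI.D has it recommend on expansion, and SAP 2.3.2 extrapolates Pilot accrual to the full study. If the sites were picked for high yield, a flat per-site extrapolation would be too high. If their pools are smaller than those of the top 27, it would be too low. A mark that every site must meet is also governed by the weakest site, so one small centre could make a feasible trial look infeasible.

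**Working it through.** **1. Reproduce the plan's totals.** Sorting the 40 rows of Table 18 by CHF without ICD gives 18,353 (top 20), 22,364 (top 27), 23,929 (top 30) and 27,956 (all 40). All four match the table, so the ranking rule is read correctly.

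**2. Ranks and pools.** Pool = 0.30 × CHF without ICD + SHF without ICD.

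| Site | CHF | SHF | Rank by CHF | Pool | 16 as share of pool |
|---|---|---|---|---|---|
| Gainesville | 1,081 | 31 | 6 | 355.3 | 4.5% |
| Minneapolis | 850 | 54 | 9 | 309.0 | 5.2% |
| Nashville | 739 | 34 | 11 | 255.7 | 6.3% |
| Portland | 735 | 61 | 12 | 281.5 | 5.7% |
| Palo Alto | 536 | 21 | 26 | 181.8 | 8.8% |
| Washington | 292 | 2 | 40 | 89.6 | 17.9% |

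Palo Alto is inside the top 27, whose lowest count is 529. Washington is not.

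**3. Averages.**
- Six sites: 1,472.9 / 6 = 245.5.
- All 40: (0.30 × 27,956 + 828) / 40 = 230.4.
- Top 27: (0.30 × 22,364 + 623) / 27 = 271.6.
- Five sites without Washington: (1,472.9 − 89.6) / 5 = 276.7.

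The six fall below the top-27 mean because of one centre.

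**4. If recruitment were proportional to pool (an assumption).** The full stage needs 1,360 / (27 × 3) = 16.79 patients per site-year, or 16.79 / 271.6 = 6.18% of the pool each year. Applied to the six sites:
- Expected total: 0.0618 × 1,472.9 = 91.1.
- By site, in table order: 22.0, 19.1, 15.8, 17.4, 11.2 and 5.5.
- Flat extrapolation: 91.1 / 6 × 81 = about 1,229, against 1,360 needed, an apparent shortfall of about 10%.

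With independent Poisson counts at 1.5 times that yield, all six sites reach 16 with probability 0.7%. The five without Washington do so with probability 58%.

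**5. How much of this is due to Table 18?**
- With equal rates of 17 per site and no link to pool, P(Poisson(17) ≥ 16) = 0.6285, and 0.6285^6 = 6.2%. An every-site mark is hard to meet at exactly the planned rate whichever sites are chosen.
- Six sites at the needed average would enrol 6 × 16.79 = 100.7. The gap from 91.1 is 9.6, and one Poisson standard deviation is √91.1 = 9.5. One Pilot year could not reliably separate the two.
- Nashville, the third site below 16, is at 15.8 and has a 51% chance of reaching the mark. At a CHF share of 22%, the low end of protocol Table 16, it moves to 16.1.
- The 17.9% depends on the FY2009 count. XVI.A.1.e gives more than 440 patients per site per year. Scaling Washington by 440 / 271.6 gives 16 / (89.6 × 1.62) = about 11%. The relative sizes of the sites do not change.

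**6. Can the DMC compare sites with a projection?** SAP 2.1 assumes 17 patients at each of six sites. SAP 2.3.2 uses 17 per site per year as its prior. The accrual dataset in SAP 3.5 holds targeted against actual randomization by month and by site. Seventeen a year, pro-rated, is the natural entry for the blank column.

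**The case for a change.** The best case for acting is that XII.D makes the method of selection its reason for the mark and then leaves that method unstated, while the only site-level evidence points the other way for Washington. The remedy looks cheap: six projected numbers, a column definition, and a second extrapolation scaled by pool beside the flat one.

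Part of this stands. The basis for selection is not given in the text supplied (the appendices were not available), and Table 18 does not support the description for Washington and supports it only weakly for Palo Alto.

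The rest does not carry. Table 18 counts FY2009 diagnosis codes, and a low count does not contradict a high recruitment projection. Protocol VIII.A.2 says patients are routinely referred to implanting centres from distant facilities and may not yet be in the centre's records, so a site's count can miss part of its catchment. The planning committee list places members, including the principal proponent, at Washington and others at Portland, Minneapolis and the health system whose station number SAP Table 2 gives to Nashville. The documents do not state this as the ground for selection, but it shows that the planners knew more about these sites than Table 18 records.

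The pool-scaled projection is no clear gain. From a Pilot of 102 it gives 102 / 1,472.9 × 271.56 × 81 = about 1,523, against 102 / 6 × 81 = 1,377 per site. It would be too high if the sites were in fact chosen for yield, and it needs Table 18 brought up to date, which means repeating the six-database search. SAP 2.3.2 already allows a multicentre Bayesian projection with a credible interval.

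**Conclusion.** The ranks are right, but the conclusion drawn from them is too strong. On FY2009 counts, and if the six sites in SAP Table 2 are the Pilot sites, one site (Washington, 40th of 40, pool 89.6) is a real outlier and one (Palo Alto, 26th) is modest. The other four rank 6th to 12th. This does not show a wrong selection, because Table 18 measures coded patients. The striking probabilities need recruitment proportional to those codes, which the documents do not claim, and the 6.2% chance under equal rates arises without any use of Table 18.

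The DMC has a stated target of 17 per site per year and a dataset that compares it with actual intake. XII.D attaches no automatic go/no-go consequence to the mark, and XI.D leaves the recommendation on expansion to the DMC's judgement. A sensible reader would weigh a miss at Washington alone against its small coded pool. What remains is an unstated basis for site selection, which a sentence in XII.D could supply if the sponsor wished. The mark, the target and the analysis would stay as they are, so no change to the plan follows.

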We hereby submit this revised protocol for CSP-592 following review by the Central Institutional Review Board (CIRB), and the convening of our Pre-Kick Off meeting; both occurring last month. Following extensive collaboration on the part of the Executive Committee and the staff at the Coordinating Center, we have refined our study and Protocol. The objective of the full study phase is to determine the survival benefit of the internal cardioverter defibrillator (ICD), as an additive therapy on top of Optimal Medical Therapy (OMT) in patients greater than or equal to 70 years old with systolic heart failure and reduced ejection fraction. We hypothesize that the OMT + ICD will reduce all-cause mortality compared to OMT without device. The objective of the Pilot study is to determine the feasibility of recruitment for the full study phase. We summarize the changes in greater detail in an accompanying Impact Statement, and submit to you at this time two copies of this Protocol: 1) a tracked-changes version, and 2) a "clean" copy of the latest version.

The Pilot phase will operate at 6 sites for 1 year; with a target of recruitment of 102 participants. If the study proves feasible during the Pilot, and is approved by CSP to continue, Phase 2 would expand to a five-year study with a full complement of 27 sites, with 3 years of intake and a minimum of 2 years of follow-up. Seeking a 25% reduction in the hazard ratio (23.5% relative risk reduction) and a 2-sided alpha of $p < 0.05$, a sample of 1,462 patients is needed.

The study is very important not only to our Veterans but to the public as well. The results of this study whether positive or negative will undoubtedly change the practice of medicine.

Thank you for your support of this study,

Sincerely

A handwritten signature in blue ink, appearing to read "[name]".

[name].
Study Proponent

< This page left intentionally blank >

Director: Cooperative Studies Program Coordinating Center

DEPARTMENT OF VETERANS AFFAIRS
VA Connecticut Healthcare System
[name]
[name]
COOPERATIVE STUDIES PROGRAM COORDINATING CENTER

In Reply Refer To: 689/151A

February 20, 2015
[name], PhD
Acting Chief Research and Development Officer
VA Central Office
[name]
[name]

Dear [name]:

Attached is a revision of CSP #592, "Efficacy and Safety of ICD Implantation in the Elderly" from the Principal Proponent, [name] and the Study Biostatisticians, [name], and [name].

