A participant may choose to withdraw from the study at any time. If a participant withdraws or is permanently lost to follow-up, a Study Exit Form will be completed. The study will employ an intention-to-treat analysis, i.e. participants will be analyzed as randomized whether or not they receive their protocol-assigned treatment. Patients who wish to withdraw from treatment, e.g., decide against the ICD implant after randomization, request that ICD implant be explanted or disabled, or for those enrolled to the OMT who receive an ICD implant in the follow-up period, will be asked to still complete all follow-up contacts. If a participant withdraws consent to be followed, the person will be withdrawn from further study except for the collection of publicly available data, e.g. survival data. When participants consent to enroll they will be informed that the collection of survival data from public record sources will continue even if they withdraw from follow-up. All other data collected up to the point of withdrawal will be used in the analyses; study follows an “intention-to-treat” design: in the case of ‘cross-over,’ any patient will be included in the group to which they were assigned.

D. Study Termination and Closeout

The VA Cooperative Studies Program, as the sponsor of the trial, may stop the study at any time based on funding issues or internal or external evidence that the study is no longer feasible or ethical to continue. The Data Monitoring Committee will be the only group that can review unblinded outcome data and can at any time recommend to the sponsor that the trial be terminated because of efficacy, safety, or futility. The DMC will also make a recommendation to Central Office whether to expand the study from Pilot stage to its planned Full-Scope. The Executive Committee, in consultation with the Data Monitoring Committee and the CSP

Director, can also terminate individual sites from participation in the trial. If a site or the entire trial is terminated, participating sites will be notified and given a closeout plan and a schedule at that time.

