	NYHA Class III	0.37 (0.15 – 0.90)
Bardy 2005 ²⁹	All patients	0.77 (0.62 – 0.96)
	Ischemic Chronic Heart Failure	0.79 (0.60 – 1.04)
	Non-Ischemic Chronic Heart Failure	0.73 (0.50 – 1.07)
	NYHA Class II	0.54 (0.40 – 0.74)
	NYHA Class III	1.16 (0.84 – 1.61)
Chan 2009 ⁵³	>75 years	0.59 (0.39 – 0.90)
Santangeli 2010 ⁶²	>60-65 years (meta-analysis)	0.75 (0.61 – 0.91)
Kong 2011 ⁷⁰	>75 years (meta-analysis)	0.73 (0.51 – 0.97)

The hazard ratio for effect of ICD therapy on all-cause mortality varies widely, primarily because of the differences in the populations analyzed in the various clinical trials. For this reason, it is a challenge to identify specific clinical trials on which to base our effect size assumption. However, two meta-analyses have been published that assess the impact of ICD on the elderly. In the assessment of the MADIT-II, DEFINITE, DINAMIT, SCD-HeFT and IRIS studies, a Hazard Ratio of 0.75 (95% CI 0.61 to 0.91) was found⁶²; and in a separate analysis of MADIT-I, MUSTT, MADIT-II, DEFINITE, and SCD-HeFT, a Hazard Ratio of 0.73 (95% CI

0.51 to 0.97) was found ⁷⁰. These Hazard Ratios are similar, and based on a sufficiently broad literature basis that they are the best point estimates of expectation for CSP #592. This study will adopt the more conservative of the two estimates, i.e. Hazard Ratio of 0.75.

2. Projected Sample Size

The following assumptions were used for the sample size calculation:

- Two-sided Type I error of 0.05
- Pilot stage with uniform recruitment over 1 year, with uniform follow-up of 5 years for all participants; 17 participants per site at 5 sites, i.e. $17 \times 5 = 85$ patient follow-up years
- Full-scale stage with uniform recruitment over 3 years (minimum follow-up = 2 years, maximum follow-up = 5 years, median follow-up = 3.5 years)
- Annual event rate of 15% in the control arm
- Hazard ratio of 0.75 (relative risk reduction = 23.5%)
- Allocation ratio of 1:1 for the treatment groups
- Annual drop in rate of 2.5% from the control group to the ICD group
- Drop-out rate of 1% from the ICD group to the control group in year 1 only.
- Annual loss-to-follow-up of 1%

Annual Event Rate in the Control Arm	Hazard Ratio		
	0.70	0.75	0.80
12%	1,177	1,771	2,881
15%	971	1,462	2,384
18%	834	1,258	2,057

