2.1 Study Design Summary

The primary outcome of CSP#592 is all-cause mortality analyzed as time to event. The primary hypothesis is that the ICD arm will have a 25% reduction in the hazard ratio (HR=0.75) (23.5% relative risk reduction in the annual mortality rate). The sample size calculation assumes a 15% annual mortality rate in the control arm. The cumulative event rate by the end of the 5-year trial (3.6 years average follow-up¹), taking into account administrative censoring, loss, drop-in, and drop-out, is projected to be 42.0% in the control arm versus 34.1% in the ICD arm. The following assumptions were used for the sample size calculation:

- Two-sided Type I error of 0.05
- Pilot stage with uniform recruitment over 1 year, with uniform follow-up of 5 years for all participants; 17 participants per site at 6 sites, i.e. $102 \times 5 = 510$ patient follow-up years
- Full-scale stage with uniform recruitment over 3 years (minimum follow-up = 2 years, maximum follow-up = 5 years, median follow-up = 3.5 years)
- Annual event rate of 15% in the control arm
- Hazard ratio of 0.75 (relative risk reduction =23.5%)
- Allocation ratio of 1:1 for the treatment groups
- Annual drop-in rate of 2.5% from the control group to the ICD group

¹ Five years follow-up for Pilot Study participants (N=102), plus 3.5 years average follow-up for participants in Stage II (N=1360): $(5 \times 102 + 3.5 \times 1360) \div (102 + 1360) = 3.6$ average years of follow-up.

- Drop-out rate of 1% from the ICD group to the control group in year 1 only.
- Annual loss-to-follow-up of 1%

Because the VA Vital Status File will be searched for all deaths, loss-to-follow-up for the primary endpoint is considered to be very negligible and was therefore not accounted for in the sample size calculation. Based on a 15% annual event rate in the control arm and a hazard ratio of 0.75, and the other assumptions listed above, a sample size of 1,462 (565 total primary outcome events) will be needed in order to achieve 90% power with a 2-sided Type I error rate of 0.05.

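### The only numerical pilot feasibility criterion requires each of six sites to enrol at least 16 patients, so a pilot whose true rate is the planned 17 per site would usually miss it

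*Combined protocol and SAP*

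**What the plan says.** The February 2015 letter from the principal proponent sets the size of the pilot: "The Pilot phase will operate at 6 sites for 1 year; with a target of recruitment of 102 participants". SAP 2.1 agrees ("17 participants per site at 6 sites"). The sample-size assumptions in protocol XV.A.2 say "17 participants per site at 5 sites" instead, which looks like a leftover that needs aligning.

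Protocol XII.D gives the criterion. It opens with a reason, "Since the Pilot study will be operating at six sites selected on the basis of projected high recruitment", and continues that "all sites within the Pilot study must meet at least 90% of the target enrollment of 17 patients within the first year". Meeting it, the section says, "will provide evidence of study feasibility in full-scale operation over a wider range of sites". For main-phase sites the same section is looser and cites early ramp-up: a site is considered for probation or reduced funding if it enrols fewer than four in six months or fewer than twelve in the first year.

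The expansion decision is described elsewhere. Protocol XI.D says: "The DMC will also make a recommendation to Central Office whether to expand the study from Pilot stage to its planned Full-Scope". The proponent's letter makes continuation subject to CSP approval. Neither place cites the 90% figure or gives another number. SAP 2.3.1 states that the pilot's objective is feasibility of recruitment. SAP 2.3.2 plans to predict full-study accrual by direct extrapolation and mentions a possible Bayesian prediction with a credible interval. Neither SAP section sets a threshold.

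**The concern.** The criterion is a condition on the minimum of six site counts. Site counts vary by chance, and the minimum of six falls well below their common mean even when every site recruits at the planned rate. The rule makes no allowance for this.

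It also measures something other than what the full trial needs. The protocol's research plan describes an average of 17 per site per year. The footnote in XV.A assigns 1,360 participants to the full-scale stage. Over 27 sites and 3 years that is 1,360 / (27 × 3) = 16.8 per site per year on average. Weak sites are foreseen, and XII.D allows centres to be dropped, added or replaced. Yet six pilot sites could together enrol 102 or more and still miss the criterion because one of them enrolled 15.

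At stake is how the pilot result is read. If the only written benchmark would usually be missed by a pilot that supports the full trial, the DMC must either treat an adequate pilot as short of target or set the benchmark aside after seeing the data.

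**Working it through.** **Inputs from the documents.** Six pilot sites, a target of 17 per site per year and a threshold of 90% of target (XII.D); pilot target 102 (proponent's letter).

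**Assumption not in the documents.** Site counts are independent Poisson with the same true mean. Variants are shown below.

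**1. The plan's own figure.** 6 × 17 = 102, which reproduces the stated target.

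**2. Threshold.** 0.9 × 17 = 15.3, so at least 16 whole patients per site.

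**3. Base case, true mean 17.**
- One site: P(X ≥ 16), X ~ Poisson(17), = 0.6285.
- All six: 0.6285^6 = 0.062.
- Criterion missed: 1 − 0.062 = 0.938, about 94%.
- Expected number of sites falling short by chance: 6 × (1 − 0.6285) = 2.2.

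**4. Sensitivity to the assumption (mean 17 throughout).**

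| Variant | Criterion missed |
|---|---|
| Poisson, threshold rounded down to 15 | 86.2% |
| Total fixed at exactly 102, split at random | 99.3% |
| Same, threshold 15 | 93.4% |
| Between-site CV 0.1 / 0.2 / 0.3 / 0.5 (negative binomial) | 94.6% / 96.0% / 97.2% / 98.5% |
| Less variable counts: binomial, 52 / 26 slots | 91.3% / 84.1% |
| Five sites, as in XV.A.2 | about 90% |

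These run from roughly 84% to 99%. The figure drops clearly below that only if counts are far more regular than ordinary accrual. A binomial with 20 slots, whose variance is 20 × 0.85 × 0.15 = 2.55 against 17 for Poisson, gives 67%.

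**5. Sites that recruit above target (Poisson, threshold 16).**

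| True mean per site | One site passes | All six pass | Missed |
|---|---|---|---|
| 18 | 0.713 | 0.132 | 87% |
| 20 | 0.844 | 0.360 | 64% |
| 22 | 0.923 | 0.619 | 38% |
| 24 | 0.966 | 0.811 | 19% |

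For a 50%, 80% or 90% chance that all six pass, the true mean must be about 21.1, 23.9 or 25.6. The 80% figure is 23.9 / 17 = 1.41 times the target.

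**6. A pooled criterion for comparison.** 0.9 × 102 = 91.8, so at least 92 in total. With the total Poisson at six times the site mean:

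| True mean per site | Pooled ≥ 92 met | All six ≥ 16 met |
|---|---|---|
| 17 | 85% | 6.2% |
| 14 | 20% | 0.1% |
| 13 | 7% | below 0.1% |

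With an assumed between-site CV of 0.2 or 0.3, the pooled criterion is met about 79% or 74% of the time at a mean of 17. The pooled rule separates adequate from inadequate recruitment. The all-sites rule is rarely met in either case.

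**The case against.** **The criterion is not a written stopping rule.** This stands. A reader might infer that a pilot missing the mark in XII.D fails and the trial ends there. The text does not say so. Meeting the criterion is described as evidence of feasibility, in a section on site intake and probation; the DMC then recommends and CSP approves.

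**Something remains if the criterion is set aside.** This also stands. A reader might infer that the DMC would then have nothing to work from. SAP 2.3.2 plans a trial-level accrual extrapolation, and protocol XV.B.1 gives the DMC overall and by-site recruitment reports. Neither carries a numerical cut-off, and the Bayesian interval is only something the study may test.

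**The stricter bar is deliberate.** Pilot sites were picked for projected high recruitment, so their true means may exceed 17. This softens the 94% but does not rescue the rule: at a mean of 20 it is still missed about 64% of the time, and the documents project no pilot rate above 17.

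**If every site enrols exactly 17, all pass.** True, but that supposes no random variation. Here on target means a true rate of 17, and the 94% depends on the assumed distribution.

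**The pooled threshold is one choice among several.** Fair. It would be missed about 15% of the time at 17 per site and met about 20% of the time at 14, a rate that would give about 84 + 14 × 27 × 3 = 1,218 of 1,462 participants. Other cut-offs can be defended.

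**Conclusion.** The concern holds as a fault in the stated criterion. With a true mean of 17 per site and independent Poisson counts, the only numerical pilot feasibility criterion would be missed about 94% of the time (roughly 84% to 99% under the main alternatives), and about 64% of the time at a mean of 20. The exact figure rests on an accrual distribution that the documents do not give. The direction does not, unless site counts are implausibly regular. The ramp-up that XII.D itself expects would make a miss more likely.

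The documents do not support the stronger conclusion that the plan would declare a feasible trial infeasible. The consequence is narrower: the pre-stated benchmark carries little information about the average rate on which the full trial depends. The type I error, primary analysis and participant safety are untouched. It is worth correcting before pilot recruitment is judged, but it is not among the most serious faults a plan can have.

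**What to change.** In XII.D, state the pilot feasibility criterion on the pooled count, for example at least 92 of 102 participants randomised across the six sites in the first year. Say that the DMC will weigh it together with the accrual projection in SAP 2.3.2, and cross-refer to it from XI.D. Use per-site counts, such as the main-phase thresholds, only to trigger site review. If another cut-off is preferred, give its chance of being met at 17 per site and at a rate the sponsor regards as inadequate. Align the pilot site count in XV.A.2 with the six used elsewhere.

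The main change is about one sentence, with no effect on endpoints, sample size or analysis. The downside is that a weak site can be offset by stronger ones, which is also how the main trial would recruit; the site-review trigger keeps such a site visible.
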